3.9 Quality of Life

The analysis of QOL will be conducted for the ITT population.

3.9.1 Measurements of Quality of Life

Generic and disease-specific measures will be used to assess QOL. Questionnaires will be completed at enrollment and every 3 months during the screening period, then at day 75 and months 6 and 12 following transplant.

3.9.2 Generic Measure

3.9.2.1 Version 2 SF-36 survey

The version 2 SF-36 health survey, standard (4-week) recall form will be adopted for general QOL measure in this study. This widely used, generic instrument derives eight scales (physical functioning, role-physical, bodily pain, general health, vitality, social functioning, role-emotional, mental health) and two summary components (physical and mental).

3.9.2.2 European Quality of Life Questionnaire

The EQ-5D is a public domain instrument. This instrument is a utility measure that generates a descriptive profile and single index value for health status. The descriptive portion addresses five health dimensions (mobility, self-care, usual activities, pain/discomfort, and anxiety/depression). The second portion of the EQ-5D is a (0-100) visual analogue scale that is used to report overall health status.

3.9.3 Disease-Target Measures

3.9.3.1 Diabetes Distress Scale

The DDS represents the latest iteration of the Problem Areas in Diabetes (PAID) scale. This is a 17-item self-administered questionnaire selected from a longer battery of 28-items.

3.9.3.2 Hypoglycemia Fear Scale

The HFS is a 23-item self-administered survey for measuring the fear experienced with respect to hypoglycemia. The HFS has two subscales. The first measures hypoglycemia avoidance behavior, and the second measures worry about hypoglycemia.

3.9.4 Statistical Analyses of Quality of Life

The general analysis procedure is as follows:

1. We will estimate the mean QOL score and its 95% confidence interval at 75 ± 5 days following the initial and final islet transplant.
2. We will estimate the mean QOL score and its 95% confidence interval at 365 ± 14 days following the initial and final islet transplant.
3. We will compare the QOL score at three time points: baseline, 75 ± 5 days following the initial islet transplant and 365 ± 14 days following the initial islet transplant.

3.9.4.1 Analysis for SF-36 survey

3.9.4.1.1 *Analysis at 75 ± 5 days following the initial and final islet transplant*

We will compute the Summary Physical Component (SPC) and Summary Mental Component (SMC) from the version 2 SF-36 health survey form at 75 ± 5 days following the initial and final islet transplant (if applicable). For both SPC and SMC, we will calculate the sample mean and construct the 95% confidence interval of the mean value using the method for a continuous variable described in SAP section 3.6.3. We will also compute the change from baseline for both scores and analyze the changes using the same method.

3.9.4.1.2 *Analysis at 365 ± 14 days following the initial and final islet transplant*

Obtain the SPC and SMC scores from the version 2 SF-36 health survey form at 365 ± 14 days following the initial and final islet transplant (if applicable).

For both SPC and SMC, we calculate the sample mean and construct the 95% confidence interval of the mean value using the method for a continuous variable described in SAP Section 3.6.3.

3.9.4.1.3 *Comparison of SPC and SMC at three time points*

For each subject, we will obtain his/her score at baseline, 75 ± 5 and 365 ± 14 days following the initial islet transplant. The analysis adopts the method of linear mixed models with a term for time (baseline, 75 days following the initial islet transplant and 365 days following the initial islet transplant) and repeated measures on subjects.

The analysis proceeds as follows:

The Shapiro-Wilk test is applied to test the hypothesis that the QOL score is normally distributed. If the normality hypothesis is not rejected at significance level 0.05, a linear mixed model analysis will be performed to test whether the mean QOL score is the same among the three time points. This model will include a term for time (baseline, 75 days, and 365 days) with repeated measurements on subjects.

The results would be treated as follows:

- 1) If the p-value is greater than 0.05, we conclude there is no evidence to claim the difference of the QOL score from the baseline.

- 2) If the p-value is less than 0.05, we would compute the overall 95% confidence intervals for the pair-wise differences in the QOL score between any two time points using the Bonferroni adjustment for multiple tests.

If the normality hypothesis is rejected at significance level 0.05, we will use the bootstrap procedure (sampling subjects with replacement) to construct the overall 95% confidence interval of the pair-wise difference in the QOL score between any two time points using the Bonferroni adjustment for multiple tests.

We will use this to compare the difference at the three time points for both SPC and SMC. Any change in SPC or SMC from baseline may be due to the intervention or it may be due to regression to the mean. Because there is no control group, causality cannot be inferred.

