observe a rate larger than 70%. With a sample size of 48 transplanted subjects, 31 subjects (65%) would need to achieve a favorable outcome for the exact 95% lower confidence bound to rule out a 50% or lower true rate. (This result is not shown in the table; 65% favorable outcome rate of 48 subjects transplanted results in 31 successfully transplanted subjects). The proposed sample size is 48 subjects. Each participating center is expected to enroll at least 6 subjects.

Table 3 displays the probability that the study would conclude that the true favorable outcome rate is at least 50% for several selected values of the true favorable outcome rate. The tabulated probabilities are the power that a one-sided binomial test of the null hypothesis $H_0: p < 0.5$ versus the alternative hypothesis $H_a: p \geq 0.5$ would conclude that the true favorable outcome rate is at least 50% given that the selected value is the true underlying favorable outcome rate. These values are obtained by calculating the binomial probability that at least 31 out of 48 total enrolled subjects would achieve the favorable outcome given the true outcome rate.

Table 3- The power to rule out a favorable outcome rate that is less than or equal to 50% for the given true favorable outcome rate.

True Favorable Outcome Rate	Power to Rule Out Favorable Outcome Rate
10%	0.0000
20%	0.0000
30%	0.0000
40%	0.0005
50%	0.0297
60%	0.3111
70%	0.8359
80%	0.9962
90%	1.0000

This table shows that if the true favorable outcome rate is 70%, the power of concluding that the rate is over 50% is 0.8359 for a 5% level test.

3. General Analysis Definitions

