3.7.2 Statistical Analyses of Secondary Endpoints

Except for the primary analyses there are no explicit or implied hypotheses in the protocol. Changes in the secondary outcomes are of interest as they will relate to efficacy as measured by the primary outcome variable. All analyses are descriptive and are intended to document the changes in these important variables. Secondary outcomes will be used to support the decision for efficacy of islet transplantation in this population but are not intended to be used explicitly for making a decision for the efficacy of islet transplantation in this population.

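### The three-visit quality-of-life comparison gives intervals for change only after p<0.05 if scores pass a normality test, but always if they fail it

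*SAP*

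**What the plan says.** The rule is in SAP section 3.9.4.1.3 and has two branches.

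- **Normal branch.** "If the normality hypothesis is not rejected at significance level 0.05, a linear mixed model analysis will be performed", testing whether the mean score is equal at baseline, Day 75 and Day 365. Two outcomes follow. Either "If the p-value is less than 0.05, we would compute the overall 95% confidence intervals for the pair-wise differences in the QOL score", with a Bonferroni adjustment, or "If the p-value is greater than 0.05, we conclude there is no evidence to claim the difference of the QOL score from the baseline". In the second case no interval is specified.
- **Non-normal branch.** "If the normality hypothesis is rejected at significance level 0.05, we will use the bootstrap procedure (sampling subjects with replacement) to construct" Bonferroni-adjusted pairwise intervals. No preliminary test of the three means is required.

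Sections 3.9.4.2.3 (OHS), 3.9.4.3.3 (DDS) and 3.9.4.4.3 (HFS) all refer back to 3.9.4.1.3.

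Two other parts of the plan bear on the point. Section 3.9.4.1.1 analyses change from baseline in the SF-36 physical and mental summary scores (SPC, SMC) at Day 75 by the continuous-variable method of 3.6.3, which yields a 95% interval whatever any p-value. For every scale, sections 3.6.5 and 3.9.4 also give the mean score with a 95% interval at baseline, Day 75 and Day 365. Those intervals are for levels, not for changes.

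On the purpose of the secondary analyses, section 3.7.2 says: "All analyses are descriptive and are intended to document the changes in these important variables".

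**The concern.** Whether a reader sees an interval for change depends on two preliminary tests, and neither bears on whether the change should be documented. Of two scales with the same mean change, one could be reported with an interval because its scores are skewed, and the other without one because they are not.

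On the normal branch the filter works against the stated descriptive purpose. A small or null change is where an interval is most useful, because it shows how large a change can still be excluded, and that is where the plan supplies none. Conversely, an interval that passes the filter belongs to an estimate that was large enough to be significant, so on average it overstates the true change when that change is small.

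Elsewhere at Day 365 the SAP analyses change from baseline without any such condition: HbA1c (3.7.6.2), Clarke score (3.7.6.5), HYPO score (3.7.6.6) and β-score (3.7.6.8). Quality of life is treated differently, and no reason is given.

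**Working it through.** **Which changes have a guaranteed interval**

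| Score | Day 75 minus baseline | Day 365 minus baseline |
|---|---|---|
| SPC, SMC | Yes (3.9.4.1.1) | Only through 3.9.4.1.3 |
| OHS | Only through 3.9.4.1.3 | Only through 3.9.4.1.3 |
| DDS | Only through 3.9.4.1.3 | Only through 3.9.4.1.3 |
| HFS | Only through 3.9.4.1.3 | Only through 3.9.4.1.3 |

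The visit means do not fill the gaps. With complete data their difference is the mean change, but an interval for a paired change also needs the within-subject correlation, which separate intervals for levels do not give.

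**Inputs from the plan**

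- Sample size, section 2.4: "The proposed sample size is 48 subjects". As a check, the exact binomial probability of at least 31 successes in 48 is 0.8359 at a true rate of 0.70 and 0.0297 at 0.50. Both agree with Table 3, including the statement "if the true favorable outcome rate is 70%, the power of concluding that the rate is over 50% is 0.8359". The present point does not rest on that figure, and the quality-of-life sections give no numerical figure to reproduce.
- Three visits, omnibus test at 0.05, three pairwise intervals with Bonferroni adjustment.

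**Assumptions not in the plan**

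Complete data, normal scores with unit SD and equal correlation between visits of 0.4 to 0.6, and a true Day 365 change of 0 to 0.5 SD with half of it present at Day 75.

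**Formulas**

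- The omnibus F test has 2 and 2 × (48 − 1) = 94 degrees of freedom. With complete data this is equivalent to the random-intercept mixed model.
- Each pairwise interval is the estimate ± t × √(2 × MSE / 48), where t is the upper 0.05/6 point on 94 degrees of freedom, 2.438. The nominal level of each interval is 1 − 0.05/3 = 98.3%.
- The expected MSE is 1 − correlation, so the half-width is about 2.438 × √(2 × 0.6/48) = 0.39 SD at correlation 0.4 and 2.438 × √(2 × 0.4/48) = 0.31 SD at correlation 0.6. This is the information withheld when the omnibus test is not significant.

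**Results on the normal branch** (20,000 simulated trials per setting; each range spans the correlations)

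| True Day 365 change | Interval reported | Mean reported estimate ÷ truth | Coverage of the Day 365 interval when reported |
|---|---|---|---|
| 0 | about 5% | not defined | 66–70% |
| 0.2 SD | 18–26% | 1.7–2.0 | about 95–97% |
| 0.3 SD | 37–52% | 1.3–1.5 | about 97–99% |
| 0.5 SD | 80–94% | 1.03–1.11 | about 99% |

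Without the condition, the Day 365 estimate is unbiased and its interval covers the truth in about 98% of trials. When there is no change it excludes zero in about 1.6%.

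**A different shape of change.** With equal change at Days 75 and 365 and correlation 0.3 to 0.7, the interval is reported in 21–42% of trials at 0.2 SD (1.4–1.9 times the truth), 41–79% at 0.3 SD (1.1–1.4 times) and 85–99.7% at 0.5 SD (1.00–1.07 times). If the intervals are always computed, the three together cover jointly in 95.4–95.9% of trials.

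**The case against.** An omnibus test followed by pairwise comparisons is a conventional protected procedure, and adding a condition cannot raise the unconditional false-positive rate. Both statements are correct. However, the Bonferroni adjustment already controls the error without the condition, so the condition adds no protection that is needed.

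The visit means are always reported, so the point change is visible for every scale whatever the p-value. This stands. What is withheld is the paired interval, and the exaggeration describes the intervals shown, not everything the plan reports.

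The magnitudes rest on assumed effect sizes. The SAP states no expected quality-of-life change, and its introduction links hypoglycemia unawareness to severe deterioration in quality of life, so a large improvement is plausible. This also stands: near 0.5 SD the exaggeration is slight. The difference between the two branches does not depend on effect size.

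Quality of life is not among the 11 key secondary endpoints, section 3.7.2 says secondary outcomes do not explicitly decide efficacy, and section 3.9.4.1.3 itself disclaims causality. This limits the priority of the point.

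A reader might also infer that the omnibus test does not address change from baseline, because a difference between Day 75 and Day 365 could trigger it. That is not so. Equality of all three means is the same hypothesis as no change from baseline at both visits. If Days 75 and 365 truly differ, at least one of them differs from baseline.

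**Conclusion.** The inconsistency is in the text and stands. In 3.9.4.1.3 the intervals for change depend on p<0.05 for scores that pass the normality test and are unconditional for scores that fail it. As a result no interval for change is guaranteed for SPC and SMC at Day 365, or for OHS, DDS and HFS at either visit. On the normal branch the intervals that do appear are selected for larger estimates. Under the stated assumptions this matters at about 0.3 SD and below and is nearly absent at 0.5 SD.

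Two stronger readings are not supported. One is that every interval for quality-of-life change is filtered by significance. Section 3.9.4.1.1 gives SPC and SMC an unconditional Day 75 change interval, and the bootstrap branch has no filter. The other is that reported intervals generally lose their stated coverage. The loss is serious only near zero change, where about 5% of trials report an interval at all.

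The primary conclusion and the key secondary tests are unaffected. Priority is low to moderate: a cheap improvement.

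**What to change.** In section 3.9.4.1.3, delete the p<0.05 condition. For every scale, always report Day 75 minus baseline and Day 365 minus baseline with Bonferroni-adjusted 95% intervals, from the mixed model or from the bootstrap if normality is rejected. Give the omnibus p-value as supporting information only. OHS, DDS and HFS inherit the change through their references to 3.9.4.1.3.

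The cost is a change of SAP wording and a few more table rows. No further data are needed.

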3.9.4.2 Analysis for European Quality of Life Questionnaire

3.9.4.2.1 *Analysis at 75±5 days following the initial and final islet transplant*

Obtain the Overall Health Status from the EQ-5D instrument at 75±5 days following the initial and final islet transplant (if applicable). We calculate the sample mean and construct the 95% confidence interval of the mean OHS using the method for a continuous variable described in SAP section 3.6.3.

3.9.4.2.2 *Analysis at 365±14 days following the initial and final islet transplant*

Obtain the OHS from the EQ-5D instrument at 365±14 days following the initial and final islet transplant (if applicable). We calculate the sample mean and construct the 95% confidence interval of the mean OHS using the method for a continuous variable described in SAP section 3.6.3.

3.9.4.2.3 *Comparison of OHS at three time points*

For each subject, we obtain his/her OHS from the EQ-5D instrument at baseline, 75±5 and 365±14 days following the initial islet transplant. We compare the difference at the three time points for OHS using the linear mixed model method described in SAP section 3.9.4.1.3.

3.9.4.3 Analysis for Diabetes Distress Scale

3.9.4.3.1 *Analysis at 75±5 days following the initial and final islet transplant*

Obtain the DDS at 75±5 days following the initial and final islet transplant (if applicable). We calculate the sample mean and construct the 95% confidence interval of the mean DDS using the method for a continuous variable described in SAP section 3.6.3.

3.9.4.3.2 *Analysis at 365±14 days following the initial and final islet transplant*

Obtain the DDS at 354 ± 14 days following the initial and final islet transplant (if applicable). We calculate the sample mean and construct the 95% confidence interval of the mean DDS using the method for a continuous variable described in SAP section 3.6.3.

3.9.4.3.3 *Comparison of DDS at three time points*

For each subject, we obtain his/her DDS at baseline, 75 ± 5 and 365 ± 14 days following the initial islet transplant. We compare the difference at the three time points for DDS using analysis of variance method described in SAP section 3.9.4.1.3.

3.9.4.4 Analysis for Hypoglycemia Fear Scale

3.9.4.4.1 *Analysis at 75 ± 5 days following the initial and final islet transplant*

Obtain the HFS at 75 ± 5 days following the initial and final islet transplant (if applicable). We calculate the sample mean and construct the 95% confidence interval of the mean HFS using the method for a continuous variable described in SAP section 3.6.3.

3.9.4.4.2 *Analysis at 365 ± 14 days following the initial and final islet transplant*

Obtain the HFS at 365 ± 14 days following the initial and final islet transplant (if applicable). We calculate the sample mean and construct the 95% confidence interval of the mean HFS using the method for a continuous variable described in SAP section 3.6.3.

3.9.4.4.3 *Comparison of HFS at three time points*

For each subject, we obtain his/her HFS at baseline, 75 ± 5 and 365 ± 14 days following the initial islet transplant. We compare the difference at the three time points for HFS using the analysis of variance method described in SAP section 3.9.4.1.3.

4. Interim Analyses and Safety Monitoring Analyses

The DSMB will be convened to review safety and efficacy data following National Institutes of Health (NIH) policy. When requested, formal interim analyses to assess safety and efficacy will be performed. Formal interim analyses will include distributions of endpoints, biomarkers and AEs. Additional analyses may be requested by the DSMB.

4.1 *Interim Analysis for Early Stopping*

This is a relatively small study; therefore, there is a need to collect as much safety data as possible, we do not plan to stop early for efficacy. We will monitor for lack of efficacy; the stopping rule will be based on excluding favorable outcome rates less than or equal to 30%.

The following table provides information on the study's strategy for stopping when the favorable outcome rate is too low. We will use the Lan and Demets [12] error spending approach with the O'Brien-Fleming [13] spending function. These calculations are based on using the O'Brien-Fleming spending function to calculate boundary values for a one-sided test of the hypothesis that the proportion achieving favorable outcome is no lower than a selected minimum value. The calculations assumed a conservative 2.5% level for the overall type I error. The procedure recommends terminating enrollment when there is overwhelming evidence that the favorable outcome rate is unacceptably low. Table 10 provides stopping boundaries for 20%, 30%, and 40% and for 3 and 4 planned analyses. It displays the numbers of favorable outcomes that would result in concluding that the true favorable outcome rate is less than the minimally acceptable rate.

For example, for three analyses and if the lowest acceptable favorable outcome rate were 20%, then the rule could not recommend stopping at the first interim analysis. It would recommend stopping at the second interim analysis (after 32 subjects had completed their one-year follow up) if none of the 32 subjects experienced a favorable outcome. The study would conclude that the favorable outcome rate was less than 20% at the end of the trial if 4 or fewer subjects experienced a favorable outcome. If the lowest acceptable favorable outcome rate were 30%, then the rule would recommend stopping at the second interim analysis if 3 or fewer subjects experienced a favorable outcome. It would conclude that the true favorable outcome rate was less than 30% after 48 subjects had completed the study if 8 or fewer subjects experienced a favorable outcome.

Table 10-Stopping Boundaries for Unacceptable Low Favorable Outcome Rates

Number of Interim Analyses	Interim Analysis	Number of Subjects	Minimally Acceptable Favorable Outcome Rate		
			20%	30%	40%
			Number Experiencing Favorable Outcome To Recommend Stopping		
3	1	16	--	--	--
	2	32	0	≤3	≤6
	3	48	≤4	≤8	≤12
4	1	12	--	--	--
	2	24	--	0	≤2
	3	36	≤1	≤4	≤7
	4	48	≤3	≤7	≤12

The Lan and Demets spending function approach allows for scheduling interim analysis as needed or requested by NIH or the DSMB. We anticipate that we will need to perform 4 interim analyses. For 4 equally spaced analyses, the stopping rule would not recommend stopping until 24 subjects have completed their one-year follow-up. At that time the rule would recommend stopping if there have been no favorable outcomes. After 36 subjects have completed their one-year follow-up the rule would recommend stopping if fewer than 5 subjects have experienced a favorable outcome. The final efficacy analysis will be adjusted to reflect the “alpha that has been spent” for these interim analyses by adjusting the confidence coefficient for the one-sided exact confidence interval for the primary outcome.

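### Table 10's three-look stopping rule at the operative 30% rate has an exact overall error of 2.86%, above the stated 2.5%; the 40% three-look rule is marginally over at 2.56%

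*SAP*

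**What the plan says.** Section 4.1 of the SAP rules out early stopping for efficacy and monitors only for a low favorable outcome rate: "the stopping rule will be based on excluding favorable outcome rates less than or equal to 30" percent. The method is named: "We will use the Lan and Demets [12] error spending approach with the O'Brien-Fleming [13] spending function". The boundaries are for a "one-sided test of the hypothesis that the proportion achieving favorable outcome is no lower than a selected minimum value", and on the level the SAP says: "The calculations assumed a conservative 2.5% level for the overall type I error".

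Table 10 gives boundaries for minimum rates of 20%, 30% and 40%, for three looks (16, 32, 48 subjects) and four looks (12, 24, 36, 48). The text works through the three-look case at 30%: "the rule would recommend stopping at the second interim analysis if 3 or fewer subjects experienced a favorable outcome", and the rate would be concluded to be below 30% "after 48 subjects had completed the study if 8 or fewer subjects experienced a favorable outcome". The 40% three-look column has 6 or fewer of 32, then 12 or fewer of 48.

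On the schedule, the SAP says: "We anticipate that we will need to perform 4 interim analyses". The four-look rule at 30% is none of 24, 4 or fewer of 36, and 7 or fewer of 48. The number and timing of looks may change at the request of the NIH or the DSMB.

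**The concern.** With 48 subjects the favorable outcome count is a small-sample binomial, and a boundary one subject too high can push the true error past its target. The three-look 30% rule is at the rate the trial uses, and it is the case that the SAP explains in words as well as in the table. A monitoring board would read the same threshold twice and take it to hold the error at 2.5%. If it does not, the chance of wrongly declaring the rate below an acceptable minimum is larger than the plan says. The error is in the direction of condemning the treatment; it cannot create a false claim of efficacy.

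**Working it through.** **Inputs**, all from SAP section 4.1 and Table 10: one-sided overall error 2.5%; O'Brien-Fleming spending; looks at 16/32/48 or 12/24/36/48; boundaries as printed. The null hypothesis is a rate no lower than the minimum, so the error is largest, and is evaluated, at a true rate p equal to that minimum.

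**Step 1. Error allowed at each look.** The usual O'Brien-Fleming-type spending function is α(t) = 2[1 − Φ(z/√t)], with z the upper 1.25% normal point (2.241) and t = n/48. For three looks the cumulative allowance is 0.01%, 0.60% and 2.50%.

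**Step 2. Exact error of a printed rule.** With no stop possible at 16, and cut-offs a at 32 and b at 48:

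error = P(X32 ≤ a) + P(X32 > a and X48 ≤ b),

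where X32 is Binomial(32, p) and X48 = X32 + Binomial(16, p). The four-look rules use the same recursion.

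**Step 3. Three-look rules as printed.**

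| Rate | Rule | At 32 | Added at 48 | Total |
|---|---|---|---|---|
| 20% | 0, ≤4 | 0.08% | 2.42% | 2.50% |
| 30% | ≤3, ≤8 | 0.55% | 2.31% | **2.86%** |
| 40% | ≤6, ≤12 | 0.91% | 1.64% | **2.56%** |

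The last row sums from unrounded terms (0.914% + 1.644% = 2.558%). A simulation with 4 million replicates gave 2.49%, 2.87% and 2.57%.

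**Step 4. Where the excess arises.**
- 30%: P(X ≤ 8 | n = 48, p = 0.30) = 2.69%. This already exceeds 2.5% with no interim look at all. The second look is in order: 0.55% against 0.60% allowed.
- 40%: P(X ≤ 12 | n = 48, p = 0.40) = 2.19%, which is acceptable alone. The excess comes from ≤6 of 32, which spends 0.91% against 0.60%.

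**Step 5. Four-look rules as printed.** Totals are 0.92% (20%), 1.43% (30%) and 2.40% (40%), all within 2.5%. Exact spending reproduces every four-look cell.

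**Step 6. Exact boundaries for three looks.** The largest cut-offs that stay within the cumulative allowances are:
- 20%: 0, ≤4 (2.50%), as printed.
- 30%: ≤3, ≤7. Error 0.55% + 0.84% = 1.39%.
- 40%: ≤5, ≤12. Error 0.28% + 1.98% = 2.26%.

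Two of the nine three-look cells change.

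**Step 7. Could a normal approximation explain the two cells?** The boundary is np − z√(np(1 − p)).
- 30%, n = 48, Lan-DeMets z = 1.993: 14.4 − 1.993 × 3.175 = 8.07. With classical O'Brien-Fleming z = 2.004 it is 8.04. Both round down to 8.
- 40%, n = 32, Lan-DeMets z = 2.511: 12.8 − 2.511 × 2.771 = 5.84. With classical z = 2.454 it is 5.998. Both round down to 5; the table prints 6.

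**The case against.** The best defence is that 2.5% is a nominal level. The SAP says the calculations assumed it and calls it conservative, which may mean only that it is stricter than the 5% one-sided level of the primary analysis. Section 4.1 does not call these boundaries exact, whereas the SAP uses that word for the primary interval. A normal-approximation boundary at nominal 2.5% that lands between 2.6% and 2.9% is unremarkable. This stands as far as it goes: 8 of 48 is not arbitrary, and restating the level as nominal is an acceptable remedy. It does not clear the text as written, which describes the overall error as conservatively set at 2.5% without mentioning an approximation.

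Three stronger readings are tempting and are not supported:
- A reader might set the four-look final boundary of 7 against the three-look 8 and call it a contradiction. It is not, because a final boundary may depend on the number of looks. The evidence is the exact error.
- A reader might attach the 2.86% to the final cut-off. That figure belongs to the whole rule; the cut-off alone has 2.69%.
- A reader might conclude that the table mixes exact and approximate methods. This is unproven. Classical O'Brien-Fleming normal-approximation boundaries, rounded down, match 20 of the 21 cells and miss the last by 0.002 of a subject; exact spending matches 19. The SAP does name Lan-DeMets spending, however, and its normal approximation would give 4.02 and 8.005 for the four-look finals at 20% and 30%, where the table prints 3 and 7.

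It is also fair that 40% is not the operative rate, and that naming Lan-DeMets already implies boundaries recalculated for the looks actually taken.

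**Conclusion.** The point holds, and it is minor. The three-look rule at 30% exceeds the stated level by 0.36 of a percentage point (2.86% against 2.5%). The 40% three-look rule exceeds it by 0.06.

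The result rests on evaluating the error at the minimum rate itself, on looks at exactly 16, 32 and 48, and on treating the boundaries as binding. The 30% finding does not depend on the form of the spending function, since the final cut-off alone is over 2.5%. The 40% second-look comparison does depend on it.

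It would be wrong to infer that the trial's expected monitoring is unsound. The anticipated four-look rule at 30% has exact error 1.43%. The disputed 30% cell applies only when all 48 subjects have completed, so no enrollment decision turns on it, and the efficacy conclusion needs 31 of 48 in any case. What remains is an incorrect threshold at the rule's own rate, printed in both the table and the text, in a schedule the SAP allows but does not expect.

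**What to change.** Recompute the three-look block of Table 10 with exact binomial Lan-DeMets O'Brien-Fleming spending at 2.5%. The 30% final boundary becomes 7 or fewer of 48 (overall error 1.39%), and the worked example changes with it. The 40% second-look boundary becomes 5 or fewer of 32 (overall error 2.26%). Alternatively, keep the printed cells, call 2.5% nominal under an approximation, and print the exact errors of 2.86% and 2.56%.

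In either case, add a sentence that boundaries will be recomputed exactly for the number and timing of looks actually taken.

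The cost is two table cells, one figure in the worked example and one sentence. The four-look block, the sample size and the primary analysis are untouched.
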